2.2 Secondary Objectives

The secondary objectives of this study are to:

- Demonstrate noninferiority for number of lesions based on a blinded read
- Evaluate confidence in diagnosis
- Compare the 0.075 mmol/kg BW dose of gadobutrol to standard dose gadoterate for:
 - T1 (longitudinal relaxation time)-weighted (T1w) MRI image quality in a paired blinded comparison
 - Sensitivity/Specificity for presence of malignant disease based on a blinded read
- Compare the overall contrast enhancement of gadobutrol (0.075 mmol/kg BW) to the standard dose of gadoterate (0.1 mmol/kg BW) for steady-state CNS imaging. Quantitative contrast enhancement will be performed using an exploratory Overall Contrast Enhancement Estimation Algorithm.
- Assess the safety profile of the reduced dose of 0.075 mmol/kg BW of gadobutrol and standard dose gadoterate after IV administration.

3. Study Design

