4.1 General Principles

The primary efficacy analyses of the 3 primary efficacy variables (visualization) will be done using the average (arithmetic mean) of the values of the 3 BRs. The analysis of these variables and the analyses of the secondary efficacy variables will also be performed on the data from the 3 BRs individually.

For border delineation, contrast enhancement, and internal morphology, there will be multiple values for each subject (ratings for multiple lesions). The average (arithmetic mean) of these ratings will be used for the primary and secondary analyses. To avoid using a scoring system that rates the detection of fewer but more well-visualized lesions over the detection of more lesions, some of which may be not so well visualized, the analysis will be performed using zero-filled averages of the ratings for each subject.

In cases where the scans detect different number of lesions, enough zeros will be included with the scores for the modalities which detected fewer lesions to make the average for each modality based on the same number of scores. This zero-filled average will always reward the detection of extra lesions. This computation of zero-filled averages means that in cases where modalities (by the BRs) detect for any of the three parameters a different number of lesions in the unenhanced and enhanced image set, enough zeros will be included for the scores in the image set in which fewer lesions were detected to make the average for each modality based on the same number of scores.

Example: A reader scores in the unenhanced image of a subject two lesions regarding internal morphology and three lesions in the combined unenhanced/enhanced images. Therefore, the subject's total score of the reader will be divided by three for both images sets.

For the comparison of gadobutrol to gadoterate, the zero-filled method will be used across contrast agents.

Example: For gadobutrol, a reader scores in the unenhanced image of a subject two lesions regarding internal morphology and three lesions in the combined unenhanced/enhanced images. For gadoterate, a reader scores in the unenhanced image of a subject two lesions regarding internal morphology and five lesions in the combined unenhanced/enhanced images. Therefore, the subject's total score of the reader will be divided by five for all image sets.

Demographic variables (age, race, sex, etc.) will be summarized using frequency tables and descriptive statistics.

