Safety variables will be summarized using descriptive statistics and frequency tables.

All confidence intervals (CIs) will be 2-sided, 95% intervals.

Any statistical tests used for noninferiority will be one-sided tests using the 0.025 level of significance.

The statistical evaluation will be performed by using the software package SAS release 9.2 or higher (SAS Institute Inc., Cary, NC, USA). All variables will be analyzed by descriptive statistical methods. The number of data available and mean, standard deviation, minimum, median, and maximum will be calculated for continuous data. Frequency tables will be generated for categorical data.

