For each parameter, a noninferiority hypothesis will be considered, where the comparison will relate to a reasonable portion (c = 0.2) of the difference between combined unenhanced/gadoterate mean and the unenhanced. The goal is to show that the loss in the visualization parameter (gadoterate minus unenhanced) – (gadobutrol minus unenhanced) is lower than 0.2 times the difference between combined unenhanced/gadoterate and the unenhanced mean. "Mean" is the mean of the BR averages.

The null and alternative hypotheses for noninferiority are:

- H_0 : (gadobutrol unenhanced gadobutrol) (gadoterate unenhanced gadoterate) $\leq -0.2*$ (gadoterate – unenhanced gadoterate) vs
- H₁: (gadobutrol unenhanced gadobutrol) (gadoterate– unenhanced gadoterate) > 0.2*(gadoterate unenhanced gadoterate).

The expression "(gadoterate – unenhanced gadoterate)" indicates the difference between combined unenhanced and gadoterate-enhanced mean vs the unenhanced mean.

The study is considered successful if all 3 hypotheses related to these co-primary target variables can be rejected each at a one-sided alpha of 0.025 or equivalently at a two-sided alpha of 0.05. Appropriate paired t-tests will be used as follows

Page: 20 of 29:

The comparisons require calculations of zero-filled averages for each co-primary target variable and each subject for

- (gadobutrol minus unenhanced gadobutrol)
- (gadoterate minus unenhanced gadoterate)

Then, for each subject and each co-primary target variable, a score is derived representing

(gadobutrol minus unenhanced gadobutrol) - 0.8*(gadoterate minus unenhanced gadoterate)

For these scores, means and standard deviations will be calculated. Appropriate t-tests will be applied. For demonstration of noninferiority, p-values will be calculated for the t-test of the working hypotheses

- H₀: (gadobutrol –unenhanced gadobutrol) $0.8*(gadoterate unenhanced gadoterate) <math>\leq 0$
- H_1 : (gadobutrol-unenhanced gadobutrol) 0.8*(gadoterate- unenhanced gadoterate) > 0

One-sided p-values will be calculated and compared to a one-sided alpha of 0.025.

No type I error adjustment for multiple comparisons is needed because tests on all 3 variables must be significant to demonstrate primary efficacy.

In addition, 95% two-sided CIs for the mean difference of the gadobutrol minus unenhanced score and the gadoterate minus unenhanced score will be calculated.

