6.2.3.2 Number of lesions able to be identified

For each image set, the BR is to record the total number of lesions, up to 10.

The number of lesions will be set to 11 for analysis purposes if > 10 lesions are reported.

For the number of lesions detected the noninferiority of gadobutrol vs gadoterate will be evaluated using tests or CIs based on the t-distribution. A noninferiority margin of 0.35 will be used in each case. This means that a 95% 2-sided CI for the mean difference gadobutrol score – gadoterate score must exceed the value -0.35 for noninferiority to be achieved.

The null and alternative hypothesis for noninferiority are:

 $H_0:$ combined unenhanced and gadobutrol MRI mean - combined unenhanced and gadoterate MRI mean \leq -0.35, vs

 H_1 : combined unenhanced and gadobutrol MRI mean - combined unenhanced and gadoterate MRI mean > -0.35,

where "mean" is the mean of the BR averages.

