6.2.3.3 Identification of benign or malignant disease

Up to 30 days post first MRI the site investigator will record in the eCRF his final clinical diagnosis, see Table 6–2 and if it confirms that the subject has malignant disease. This will serve as SOT for malignancy. A summary of final clinical diagnosis will be presented for total subjects in FAS and PPS.

The BRs will evaluate the presence of malignant lesions for each subject for the combined unenhanced and gadobutrol-enhanced MR image sets, and the combined unenhanced and gadoterate-enhanced MR image sets separately.

Page: 22 of 29:

The SOT will be compared to the blinded read evaluations individually and per majority of BRs (at least 2 out of 3 readers).

Table 6–2: Final clinical diagnosis of CNS lesions

Meningioma Chordomas • Anaplastic/malignant meningioma Primary lymphoma Glial tumor, low grade (I/II) Dermoid/Epidermoid tumors . Glial tumor, high grade (III/IV) Infectious disease (e.g., brain abscess, . cisticercosis, etc.) Glial tumor, tumor grade cannot be Venous angiomas • determined Metastases Meningeal spread of meningiomas (dural • involvement) Multiple sclerosis (acute and chronic) Cerebellopontine angle tumors . **Optic neuritis** Von Hippel Lindau syndrome Meningeal disease (focal enhancement) Hypertensive leukoencephalopathy Pituitary adenomas (macro and micro) Subacute/chronic ischemia • • Craniopharyngiomas Encephalitis • • Tumors of the choroid plexus Others, specify Tumors of the pineal gland Not assessable . Meningeal carcinomatosis Oligodendrogliomas grade II Oligodendrogliomas grade III (anaplastic/malignant)

Abbreviations: CNS = central nervous system

Diagnoses of the presence or absence of malignant tumors in each subject will be evaluated for consistency with the final diagnosis. Proportions of diagnoses consistent with the final diagnosis regarding malignancy will be calculated for gadobutrol and gadoterate, and a CI based on McNemar's test for the difference of these proportions will be given. The noninferiority of gadoterate to gadobutrol will be claimed using a noninferiority margin of 10%. These analyses will be performed for sensitivity, specificity, and overall accuracy.

Table 6–3 displays the components of the definitions for sensitivity, specificity, and accuracy.

Reader Response for MRI	Final clinical diagnosis (Standard of truth)			
	Malignant	Not Malignant		
Malignant	True positive (TP)	False positive (FP)		

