The match to final diagnosis will be always considered regarding presence or absence of malignancy.

For comparing sensitivity between modalities, the match to final clinical diagnosis refers to malignancy = yes, so n in Table 6–4 will be the total number of subjects with malignant final clinical diagnosis by the investigator (SOT).

For comparing specificity between modalities, the match to final clinical diagnosis refers to malignancy = no, so n in Table 6–4 will be the total number of subjects with benign final clinical diagnosis by the investigator (SOT).

For accuracy, the match to final clinical diagnosis refers to true positive (TP) and true negative (TN) regarding malignancy, so n will be the total number of subjects with any final clinical diagnosis by the investigator (SOT); this will be sum of the entries for each field of the tables above for sensitivity and specificity.

These tables will be produced for each reader and for the majority reader. Majority reader is defined as the value of at least two out of three readers.

Note that truth panel diagnoses of other and not assessable will be excluded from McNemar's test or calculation of McNemar's test-based CIs.

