6.2.3.5 Image quality

The BRs will evaluate the relative image quality of the gadobutrol-enhanced T1w MR images and the gadoterate-enhanced T1w MR images in a third read session different from the 2 sessions mentioned in Section 6.2.1. The assessment will be based on the overall subjective interpretation of the degree of contrast enhancement, border delineation, and internal morphology. These images will be presented in a paired fashion in a separate reading session. The gadobutrol and gadoterate images will be randomly assigned to either the left (image L) or right (image R) positions.

Image quality will be compared on a 5-point scale:

- 1 =Image R is worse
- 2 =Image R is slightly worse
- 3 =Image R is same
- 4 =Image R is slightly better
- 5 =Image R is better

After the data are unblinded, the above codes will be translated into the following scale:

- -2 = Gadobutrol image set is worse
- -1 = Gadobutrol image set is slightly worse
- 0 = Image sets are the same
- 1 = Gadobutrol image set is slightly better
- 2 = Gadobutrol image set is better

Frequency tables and descriptive statistics will be generated on these values and the combined values (Gadobutrol is better/slightly better) and (Gadobutrol is worse/slightly worse) yielding a 3 point scale Gadobutrol is better, same, or worse. The relative image qualities will be tested for equality using a Wilcoxon signed-rank test.

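### SAP 6.2.3 allows noninferiority claims on four secondary variables with no gate, multiplicity control or exploratory label, and names no deciding read for malignancy or image quality

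*SAP*

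**What the plan says.** - **Level.** SAP 4.1: "Any statistical tests used for noninferiority will be one-sided tests using the 0.025 level of significance". Confidence intervals are two-sided 95%.
- **Lesion count.** The objective in SAP 2.2 is to "Demonstrate noninferiority for number of lesions based on a blinded read". Under SAP 6.2.3.2 the interval for gadobutrol minus gadoterate "must exceed the value -0.35 for noninferiority to be achieved". The hypothesis there is written on the reader average.
- **Malignancy.** Under SAP 6.2.3.3 noninferiority "will be claimed using a noninferiority margin of 10%. These analyses will be performed for sensitivity, specificity, and overall accuracy". On the readings, "These tables will be produced for each reader and for the majority reader".
- **Image quality.** SAP 6.2.3.5: "The relative image qualities will be tested for equality using a Wilcoxon signed-rank test". The SAP gives no level for this test. Protocol 11.2.1 puts superiority tests at two-tailed 0.05.
- **Readers.** SAP 4.1 adds that "the analyses of the secondary efficacy variables will also be performed on the data from the 3 BRs individually".
- **Multiplicity.** The only statement concerns the co-primaries (SAP 3.2 and 6.2.2, protocol 11.4.1.1 and 11.5): "No type I error adjustment for multiple comparisons is needed because tests on all 3 variables must be significant to demonstrate primary efficacy".
- **Exploratory label.** Among the secondary variables, only the contrast-enhancement algorithm carries one (SAP 6.2.3.1).

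**The concern.** The co-primary argument works because all three tests must succeed together. The four secondary noninferiority claims can each succeed alone, so the argument does not carry over to them, and nothing replaces it. Nothing in the plan makes a secondary claim conditional on co-primary success.

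The second gap is the reading. For the co-primaries and for lesion count the plan names the reader average. For sensitivity, specificity and accuracy it lists three readers and a majority and does not say which one supports the claim. For image quality it names neither an average nor a majority.

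A report that followed the plan exactly could therefore state noninferiority for whichever malignancy measure passed, on whichever reading passed, even after a failed primary analysis. A reader could not tell how many chances that claim had.

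**Working it through.** **Inputs from the documents.** One-sided 0.025 per noninferiority test; four such claims (count, sensitivity, specificity, accuracy); four readings for malignancy (three readers plus majority); three readers for image quality at two-sided 0.05; 180 enrolled with about 25% non-evaluable, so 180 × 0.75 = 135.

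**Assumed, because the documents give no figure.** Malignant share 0.3 to 0.7; the correlations between variables and between readers; the discordance rates in step 6.

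**1. The plan's own level.** The lower limit of a two-sided 95% interval is a one-sided test at (1 − 0.95)/2 = 0.025. This reproduces the stated level, which applies to each test.

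**2. Why the co-primary sentence does not extend.** When all tests must reject, the chance of a false overall success is at most 0.025. When any one rejection is enough, the chance of at least one false claim lies between 0.025 and the sum of the levels, 4 × 0.025 = 0.10.

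**3. Four claims, one reading each, every null exactly at its margin.** Independent tests give 1 − (1 − 0.025)^4 = 1 − 0.9037 = 9.6%. The dependent cases were simulated:

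| Dependence | At least one false claim |
|---|---|
| Independent | 9.6% |
| Sensitivity and specificity independent (different patients), accuracy their weighted sum, count correlated 0 to 0.5 with accuracy | 7.5% to 8.2% |
| Common correlation 0.5 | 7.8% |
| Common correlation 0.8 | 5.7% |

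In the second row the accuracy statistic is √w × sensitivity + √(1 − w) × specificity, with w the malignant share. The last row is a low-end case: sensitivity and specificity come from different patients, so a correlation of 0.8 between them is hard to justify.

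**4. If a pass on any of four readings counts.** With between-reading correlation 0.9 down to 0.3, the four claims give 14% to 25%. This run also let lesion count pass on any reading, although the plan names the average for it. The figure is therefore too high for the plan as written and shows direction only.

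**5. Image quality on three readers, two-sided 0.05.** Independent: 1 − 0.95^3 = 14.3%. Simulated at correlation 0.5: 12.6%. At 0.9: 8.3%.

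**6. Cost of requiring sensitivity and specificity together.** Assume 135 patients, 40% malignant (54 malignant, 81 not), no true difference, and discordance d of 20% and 15%. Power is about Φ(0.10/√(d/n) − 1.96).
- Sensitivity: √(0.20/54) = 0.0609; 0.10/0.0609 = 1.64; Φ(−0.32) = 38%.
- Specificity: √(0.15/81) = 0.0430; 0.10/0.0430 = 2.32; Φ(0.36) = 64%.
- Both: 0.38 × 0.64 = 24%. Simulation gives 39%, 66% and 26%.

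At 10% discordance in both groups, simulation gives 54% for both.

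**The case against.** The case for leaving the plan alone is that success in this Phase 4 study is defined by the three co-primaries only. The wording about demonstrating noninferiority belongs to lesion count; sensitivity, specificity and image quality sit under a comparison objective, and accuracy is in no objective. Image quality is tested for equality, with no success rule. Lesion count names its reading, and individual-reader analyses are described as additional. All of this is correct, and it confines the several-readings point to malignancy and image quality. It does not remove the claim rules in SAP 6.2.3.2 and 6.2.3.3.

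The figures are also a boundary case. They need gadobutrol to be worse by exactly 10 points on both sensitivity and specificity and by 0.35 lesions at the same time. That objection stands, and the assumption has to be stated with the figures.

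A reader might infer two stronger things that the documents do not support.

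- *That the secondary error rate is three to four times the stated 2.5%.* The ratio can be formed (7.5/2.5 = 3.0; 9.6/2.5 = 3.9), but 2.5% is a per-test level and no family-wise rate is stated. The ratio fits only four claims on one reading each, and image quality falls under two-sided 0.05.
- *That accuracy can yield a false claim by hiding lost sensitivity.* With 40% malignant, a true 15-point sensitivity loss and equal specificity, accuracy passes in about 21% of simulated trials and sensitivity in under 1%. But the true accuracy loss is 0.40 × 15 = 6 points, inside the 10-point margin, so an accuracy pass there is a true statement. It is a reason not to rest a diagnostic claim on accuracy alone, not evidence of type I error.

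Timing also matters. The equivalence supplement to the SAP describes post-hoc examination of reader means, so a testing order chosen at that stage would not be prespecified.

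**Conclusion.** The point holds as a gap in the plan: secondary noninferiority claims without a gate, multiplicity control or exploratory label, and no deciding read for malignancy or image quality. The chance of at least one false claim among the four is about 8% to 10%, or about 6% at an assumed correlation of 0.8. This assumes one reading each and every null at its margin. It rises if any reader's pass counts.

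These figures also take each test to have its nominal size. With the standard error as corrected in the SAP supplement, simulated size at the 10-point margin was 2.7% to 5.9% for an assumed 50 to 90 patients, with 2% to 10% matching the final diagnosis on gadobutrol only. The nominal 2.5% may therefore be optimistic for sensitivity and specificity.

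The co-primary conclusion is not affected. Some SAP pages were not available, but sections 4.1 and 6.2.3, where such a rule would be expected, were.

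**What to change.** **Preferred.** State in SAP 6.2.3 that all secondary efficacy results are exploratory and reported as estimates with 95% confidence intervals, and replace the words *achieved* and *claimed*. This takes one paragraph and needs no new data, reads or patients. It is also the only sound option once results are known.

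**If formal claims are kept and the data are still blinded:**
- make secondary claims only after all three co-primaries succeed;
- keep the reader average for lesion count, use the majority reader for malignancy, and use each patient's mean of the three readers' scores for image quality (two-sided 0.05, as in the protocol);
- require sensitivity and specificity both to pass for a diagnostic-performance claim;
- control the remaining claims by a prespecified multiplicity procedure of the sponsor's choice;
- treat accuracy and individual-reader results as descriptive.

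**Cost.** Some secondary results can no longer be formally claimed. The joint sensitivity and specificity requirement has low power, about 26% under the assumptions in step 6 of the working. In a fixed sequence, placing it ahead of image quality would usually block that test, so the order needs thought.

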4.4 Handling of Nonassessable (uninterpretable) Images

For the 3 primary visualization variables, the BRs must provide a numerical score for each image set; an option for uninterpretable is not available.

For evaluation of diagnoses, the readers are given the option of "not assessable," which essentially means that the image was uninterpretable for diagnostic purposes. If this evaluation occurs for the final diagnosis, the case will be excluded from the analysis of diagnoses as no SOT is available. The rare instance of a blinded-read evaluation of "not assessable" for a diagnosis based on MRI images will be considered incorrect (not a match to final diagnosis) if a final diagnosis is available for that subject.

When the BR chooses "not assessable" for diagnosis, by definition the confidence level is 1 (not confident).

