Not Assessable	Not assessed positive (NAP)	Not assessed negative (NAN)		
Not Malignant	False negative (FN)	True negative (TN)		

Table 6–3: Components of the definitions for sensitivity, specificity, and accuracy

Sensitivity will be calculated as the number of subjects identified by MRI to have malignant lesions divided by the total number of subjects with malignant lesions according to the truth standard. Specificity will be calculated as the number of subjects identified by MRI to have no malignant lesion divided by the total number of subjects with no malignant lesion according to the truth standard. Accuracy will be calculated as the number of subjects correctly identified by MRI as having or not having malignant lesions, divided by the total number of subjects. For this analysis, a response of Benign will be considered as Not Malignant. When a response is neither benign nor malignant, then this will be considered as Not Assessable.

Using the notation of the above table,

Sensitivity = TP/(TP + NAP + FN);

Specificity = TN/(TN + NAN + FP);

Accuracy = (TP + TN)/(TP + TN + NAP + NAN + FP + FN).

Note that these calculations consider nonassessable segments as incorrect.

For the computation of the asymptotic CIs, McNemar's test-based CIs for the difference of rates between both MRI sets, the definitions in Table 6–4 are needed. With this, the standard

error of the difference between p₂ and p₁ is defined as $SE_{p_2-p_1} = \sqrt{(p_1 + p_2 - (p_1 - p_2)^2)^2 \frac{1}{n}}$

Then, the 95% asymptotic CI of the difference between p_2 and p_1 can be computed as $[(p_2 - p_1) - z_{0.975} \cdot SE_{(p_2 - p_1)}] + z_{0.975} \cdot SE_{(p_2 - p_1)}]$, with $z_{0.975} = 1.96$ as the corresponding quantile of the standard normal distribution.

Table 6–4: Components of confidence interval

Combined unenhanced/gad	Combined unenhanced diagnoses agree w		
oterate- enhanced diagnoses agree with final diagnoses	Yes	Νο	
Yes	Number of subjects with matches to final diagnosis for both MRI sets: a	Number of subjects with a match for gadoterate MRI set but not for gadobutrol MRI set: b	Proportion of subjects with a match in gadoterate MRI set: p ₁ = (a+b)/n
No	Number of subjects with a match for gadobutrol MRI set but not for gadoterate MRI set: c	The number of subjects without a match for either MRI set: d	
	Proportion of subjects with a match in gadobutrol MRI set: p ₂ = (a+c)/n		n = a+b+c+d

Abbreviations: MRI = magnetic resonance imaging.

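### SAP 6.2.3.3 drops truth diagnoses of *other* from the McNemar intervals without defining the term; on its most natural reading, subjects with a recorded malignancy status are removed by diagnosis label

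*SAP*

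**What the plan says.** SAP 6.2.3.3 compares sensitivity, specificity and accuracy for malignancy between the two combined image sets, with a 10% noninferiority margin and McNemar-based intervals. These rules bear on who is counted.

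- **Truth.** The site investigator records the final clinical diagnosis from the Table 6-2 list and "if it confirms that the subject has malignant disease". Protocol 9.2.6 likewise asks for the diagnosis and for whether it is malignant. The second item is the standard of truth (SOT).
- **Table 6-2.** The extracted text runs the two columns together, but both residual entries are there: "Others, specify Tumors of the pineal gland Not assessable".
- **n for the intervals.** For sensitivity and specificity, n is all subjects with a malignant and a benign SOT respectively. For accuracy the SAP writes "so n will be the total number of subjects with any final clinical diagnosis by the investigator (SOT"), adding that "this will be sum of the entries for each field of the tables above for sensitivity and specificity".
- **Rates.** Accuracy is the number of subjects correctly identified as "having or not having malignant lesions, divided by the total number of subjects". The three rate formulas make no exception for *other*.
- **Closing note.** "Note that truth panel diagnoses of other and not assessable will be excluded from" McNemar's test and the intervals based on it.
- **SAP 4.4.** When the final diagnosis is *not assessable*, "the case will be excluded from the analysis of diagnoses as no SOT is available". *Other* is not mentioned.

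**The concern.** The note pairs *other* with *not assessable*, and these are the two residual entries of Table 6-2. A programmer would therefore probably take *other* to be *Others, specify*. That entry is a diagnosis label and says nothing about whether the truth is known. Because malignancy is recorded in addition to the diagnosis, a subject with an unlisted tumour can have a perfectly usable malignant or benign SOT. The n definitions count that subject and the note removes them. The reason given in SAP 4.4, that no truth exists, does not apply.

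Two things are at stake. Usable subjects are lost, so the intervals widen. And because the note names only the test and the intervals, the tabulated rates and the interval for their difference may come from different subjects. Two programmers could build different analysis sets from the same page.

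**Working it through.** The plan gives no n, share of *Others*, malignant fraction or discordance rate for this analysis, so it has no figure to reproduce. The check is a comparison of the rules, followed by an illustration on assumed inputs.

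**1. The rules under each meaning of *other***

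| Rule | *Other* = *Others, specify* | *Other* = neither malignant nor benign |
|---|---|---|
| n for sensitivity and specificity | counts these subjects; the note removes them | already outside both groups |
| n for accuracy, any final diagnosis | counts them; the note removes them | outside, consistent with n as the sum of the two tables |
| SAP 4.4 | goes further: drops subjects who have a truth | same principle: no usable truth |
| Rate formulas | keep them, so rates and intervals can differ | leave them out, since Table 6-3 has only malignant and not-malignant truth columns |

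The response options of the malignancy field are in the eCRF (Final 2.0, listed in SAP section 1), which is not among the documents.

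**2. Loss of precision, first meaning only**

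The standard error is the corrected one in the SAP supplement: SE = sqrt(((b+c)/n - (p2-p1)²)/n). Here b is the number matched for gadoterate only and c the number matched for gadobutrol only. At zero difference the half-width is 1.96·sqrt(disc/n), with disc = (b+c)/n. Removing a share x at unchanged discordance multiplies it by 1/sqrt(1-x):

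- x = 0.1: 1.054
- x = 0.2: 1.118
- x = 0.3: 1.195

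The increases are 5%, 12% and 20%. Half-widths in percentage points, from 0% to 30% *Others*:

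| n before exclusion | 10% discordance | 15% discordance |
|---|---|---|
| 135 | 5.3 to 6.4 | 6.5 to 7.8 |
| 90 | 6.5 to 7.8 | 8.0 to 9.6 |
| 60 | 8.0 to 9.6 | 9.8 to 11.7 |
| 40 | 9.8 to 11.7 | 12.0 to 14.3 |

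The 135 is 180 × 0.75, from the planned enrolment and the 25% nonevaluable allowance. The other n, the discordance rates and the shares are assumptions.

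**3. Chance that the noninferiority result changes**

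Noninferiority is taken as the lower limit of gadobutrol minus gadoterate lying above -10 points. Suppose m of n subjects carry the label at random, unrelated to discordance. The discordant pairs removed then follow a hypergeometric distribution, and the limit is recomputed on n - m.

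| n, b v c | Limit, all subjects | 10% *Others* | 20% | 30% |
|---|---|---|---|---|
| 135, 7 v 7 | -5.4 | 0% (m=14) | 0.1% (m=27) | 1.2% (m=40) |
| 90, 4 v 4 | -6.2 | 0% (m=9) | 1.1% (m=18) | 9.0% (m=27) |
| 60, 3 v 3 | -8.0 | 2% (m=6) | 51% (m=12) | 43% (m=18) |

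The 51% is knife-edge. With m = 12 and no discordant pair removed, the limit is -1.96·sqrt((6/48)/48) = -10.002 points. That single outcome carries 24.5 percentage points of the probability. With m = 11 the chance is 26%.

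**The case against.** A reader might infer that the note flatly contradicts the n definitions. The text does not support that. The sentence follows those definitions and can be read as a specific exception to them. The accuracy n cannot be literal in any case: *not assessable* is also a Table 6-2 entry, and everyone agrees it is excluded. What stands is narrower. If the note is an exception by label, no reason is given for it and SAP 4.4 does not share it.

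A reader might also infer that the intervals would be built wrongly. They would not. Table 6-4 takes p1, p2 and n from one set of cells, so each interval is centred on a difference from its own data. The only possible gap is with the separately tabulated rates.

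The harmless meaning has real support. The section always matches on presence or absence of malignancy, and accuracy n is the sum of the two truth groups. The rule that turns a response that is neither benign nor malignant into *not assessable* may concern readers only, since the rows of Table 6-3 are reader responses, so it does not make *other* redundant for the truth. The mentions of a truth panel and of segments fit nothing else in this plan, so the sentence may simply be a leftover; that is an inference. Without the eCRF this meaning cannot be ruled out.

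Finally, Table 6-2 names 27 diagnoses, including the common malignant ones, and nothing in the documents supports a 20% or 30% share of *Others*. In the row with n = 40 and 15% discordance, the half-width is already 12.0 points with no exclusion. That reflects the small n and not the note. These points limit the size of the concern. They do not remove the undefined term.

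**Conclusion.** The point holds as a minor one. The note is an active exclusion rule with an undefined term. On its most natural reading it removes subjects with a known malignancy truth from the intervals, which fits neither the n definitions nor the rationale of SAP 4.4, and it lets the intervals rest on fewer subjects than the rates. On the other reading nothing changes.

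The documents do not support a claim that the noninferiority conclusion is in danger. For accuracy, with an assumed n of 135 and 7 v 7 discordant pairs, the chance of a changed result is at most 1.2% for shares up to 30%. A material chance needs a small truth group whose limit is already near -10 points. All of these figures rest on assumed n, discordance and shares, and on the label being unrelated to discordance.

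Only a secondary endpoint is involved; the three co-primary tests are untouched. SAP 6.1.4 already plans counts by final-diagnosis category, so the number of *Others* will be visible.

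**What to change.** Replace the closing note of SAP 6.2.3.3 with wording such as:

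*Subjects whose final clinical diagnosis is Not assessable (Section 4.4), or for whom the investigator recorded neither malignant nor not malignant, are excluded from the rates and from the McNemar-based CIs. Subjects with Others, specify and a recorded malignancy status are included. The same n is used for rates and CIs.*

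Replace *truth panel* with *investigator*. If excluding *Others, specify* was intended, give the reason and apply the same set to the rates.

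The supplements are labelled post hoc, and one cites observed results by agent. The change should therefore be documented as post hoc in a supplement or the study report, with the intervals shown both ways. The cost is a few sentences and one extra run of the intervals; no new data are needed.
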